**Assessing the Utility of MMPI-2-RF-EX in Detecting Simulated Underreporting of
Current Suicide Risk in Military Veterans**

NCT: 2020B0414

Study Protocol and Statistical Analysis Plan

Approved 2/25/2021

Assessing the Utility of MMPI-2-RF-EX in Detecting Simulated Underreporting of Current Suicide Risk in Military Veterans

1. Objectives

The aims of the current project are: 1) to examine the incremental predictive utility of the MMPI-2-RF-EX validity scales (L and K) in detecting simulated underreporting of suicide risk on the SUI scale and extratest measures of suicide risk (Suicide Cognitions Sale, Beck Scale for Suicide Ideation – Current) and 2) compare the use and preliminary effectiveness of a self-administered version of the Crisis Response Plan (CRP) in decreasing suicidal/death ideation and distress and increasing positive affect when compared to a clinician-administered version of the protocol in a sample of 150 military Veterans experiencing current death or suicidal ideation. Hypotheses include: **(H1)** Veterans following instructions to underreport suicide risk (Simulated Underreporting) would endorse significantly higher MMPI-2-RF-EX L and K scale scores than those administered the MMPI-2-RF-EX and extra test measures under standard conditions (Standard Instructions); **(H2)** Veterans randomized to the Simulated Underreporting group will produce significantly lower scores on MMPI-2-RF-EX (SUI) and extra test self-report measures of suicide risk (Suicide Cognitions Scale, Beck Scale for Suicide Ideation – Current) than the Standard Instructions group; **(H3)** lastly, L and K would contribute incremental predictive validity over one another in differentiating between veterans in the Standard Instructions and Simulated Underreporting group. Exploratory analyses will be conducted to examine whether those randomized to Simulated Underreporting endorse lower mean scores on extratest measures that do not assess suicide risk.

2. Background and Rationale

Military veterans comprise 7.9% of the US population but account for 13.5% of adult deaths by suicide; additionally, the Veteran suicide rate is 1.5 greater than that of the general population (US Department of Veterans Affairs, 2019). A disproportionate number of suicides are attributed to Veterans who have not recently received healthcare within the Veterans Affairs (VA) Healthcare System. Indeed, the age- and sex-adjusted suicide rates among these Veterans increased by 11.8% between 2016 and 2017, compared to an increase of 1.3% among Veterans recently utilizing VA health care services, highlighting the increasing pace of suicide rates among Veterans not receiving health care within VA, a group which constitutes the majority of Veterans (US Department of Veterans Affairs, 2019). Given the heightened suicide rate among this group of Veterans, implementation of empirically-based suicide assessment procedures would be well-served in other Veteran-serving community settings. However, research and clinical efforts to identify Veterans at highest risk of suicide have been met with limited success (Nelson et al., 2017). Further complicating suicide risk assessment in the Veteran population is the tendency for high risk populations to not disclose current levels of suicide risk (Anestis & Green, 2015). **Therefore, it is critical that empirically-derived methods of assessing suicide risk accurately identify Veterans outside the VA setting who are at risk of suicide, but do not accurately report their current experiences of suicidal ideation or intent.** However, current measures of suicide risk commonly administered in research and clinical settings are not well-suited to accomplish this task. **The proposed study is well-suited to address these limitations and expand upon preliminary findings in Veteran samples through two of its aims: 1) examine whether simulated underreporting on the MMPI-2-RF-EX (indexed by K and L scores) impacts SUI scores and generalizes to underreporting on extratest self-report measures of suicide risk and 2) assess the incremental predictive utility of MMPI-2-RF-EX L and K scales in differentiating between these groups.**

In response to enhanced detection of suicide risk, there is a need to identify psychotherapeutic interventions targeting suicide risk among military veterans who may be unable or unwilling to seek

follow-up mental health services. Indeed, reasons for refusal to seek mental health services among veterans include public and self-stigma (Held & Owens, 2013), adherence to masculine norms (Burns & Mahalik, 2011). However, Wilson et al. (2008) observed that the majority of Army soldiers who were unwilling to speak to a clinician about mental health care were willing to utilize technology-based approaches to mental health care.

2.1.1 False negatives and the current state of suicide risk assessment. The issue of false negatives in suicide risk assessment has been well-documented. In the VA setting, half of suicides occur in the group classified by physicians as being at low risk of suicide, calling the utility of suicide risk screening instruments into question (Pokorny, 1983). In accordance with Pokorny's (1983) findings, Denneson et al. (2010) observed that 72% of Veterans who died by suicide denied experiencing suicide ideation during their last suicide risk assessment by a VA provider. These findings are also consistent with those observed when suicide risk assessment is more proximal to death by suicide: Roughly 80% of suicide decedents whose death occurred in the hospital or shortly after discharge denied experiencing suicide ideation during their last suicide risk assessment (Bush, Fawcett, & Jacobs, 2003). The heightened rate of false negatives in suicide risk assessment are partly attributed to responders' concealment of suicidal intent (Nielssen, Wallace, & Large, 2017).

Suicide risk assessment is one instance in which individuals are motivated to underreport or minimize distress in order to avoid hospitalization or decrease time hospitalized (Oquendo & Bernanke, 2017; Petrik, Gutierrez, Berlin, & Saunders, 2015). Additionally, stigma related to receiving mental health care for suicide ideation (Hom, Stanley, Podlogar, & Joiner, 2016), past negative experiences related to disclosing suicide ideation (Fulginiti, Pahwa, Frey, Rice, & Brekke, 2016), negative repercussions during military service (Ganzini et al., 2013), and ambivalence about these thoughts (Harris, McLean, Sheffield, & Jobes, 2010) are other reasons for underreporting or nondisclosure of suicide ideation. Additionally, underreporting has been observed in instances when individuals are forced to select item responses (Podlogar et al., 2016; Podlogar & Joiner, 2019), which is common in clinical settings that administer self-report measures of suicide risk. Despite the documented prevalence of false negatives in suicide risk assessment and the tendency of respondents to underreport on these measures for a variety of reasons, the majority of measures and interviews assessing suicide risk are not equipped to assess underreporting. Additionally, limitations regarding the administration and interpretation of commonly administered measures of suicide risk have been noted.

While recent research has sought to identify better indicators of suicide risk using objective measures commonly administered in clinical practice (Levy et al., 2019), the design of commonly administered standardized interviews assessing suicide risk hinders the ability to accurately identify those at various levels of suicide risk (Tabares, Butner, Bryan, & Harris, In Press). Additionally, interview-based methods of suicide risk assessment rely on clinical judgment to determine an individual's current level of suicide risk and the corresponding course of intervention; however, clinicians' reliance on clinical judgment in suicide risk assessment results in heterogeneous determinations of suicide risk (Berman, Stark, Cooperman, Wilhelm, & Cohen, 2015). Further, suicide risk assessment methods that rely on clinical judgment do not add predictive validity above validated self-report measures of suicide risk (Lindh et al., 2020). In addition to the respective limitations of these methods of suicide risk assessment, each relies on patient self-report, but is not designed to accurately identify those who fail to disclose current suicide ideation or plans, preparations, or intent to attempt suicide. **This proposed research aims to address these limitations through 1) incorporating MMPI-2-RF-EX validity scales to detecting underreporting of suicide risk on the MMPI-2-RF-EX SUI scale and 2) assessing whether underreporting identified on the MMPI-2-RF-EX generalizes to extratest measures of suicide risk.**

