Participants could develop mild to moderate emotional discomfort or frustration associated with completing questionnaires or answering interview questions assessing thoughts about suicide. This potential risk is expected to be comparable to the discomfort experienced when talking with a friend or acquaintance about these same topics. If discomfort is experienced, it is not expected to be severe or to last for more than a few minutes. Participants' *confidentiality could be breached* if their identifiers are inadvertently released or accessed by a third party. This risk is expected to be low because the data are not stored or analyzed in ways that are likely to reveal a subject's identity. Breach of confidentiality could also occur if an external party or individual hacks into the Zoom interface during a participant's session. Safeguards will be implemented to mitigate this risk, including using password-protected Zoom sessions.

2.3. Benefits of the Proposed Research Results of this proposed research will have implications for future suicide risk assessment and suicide prevention efforts in Veterans through enhancing methods of identifying and responding to those at risk of suicide that would otherwise be missed by traditional methods of suicide risk assessment (i.e. false negatives).

Procedures

3.1. Research Design. A two-arm randomized controlled simulation design will be employed in this proposed research. For both components of the study, participants will be randomized using stratified blocks of 6 or 8 participants, per recommendations by Krenan et al. (1999), based on gender and suicide attempt history (no history of suicide attempts, history of one suicide attempt, or history of multiple suicide attempts).

3.2. Sample. A sample of 150 Veterans will be included in the study and randomized to study conditions (75 in the Simulation condition and 75 in the Standard condition). Results of a priori power analyses conducted using G*Power software (Faul et al., 2007) indicate that a total sample of 150 will result in a highly-powered study ($\beta = .98\text{--}.99$) to detect medium-sized effects in all regression-based analyses. Therefore, although we anticipate low attrition from this study, the proposed sample size is sufficiently powered for the proposed analyses. Additionally, this sample size accounts for a roughly 15% rate of Non-Content-Based Invalid Responding observed in other simulation-based MMPI research (Crighton et al., 2017).

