3.4. Informed Consent and Confirmation of Eligibility

Informed consent will be obtained through Qualtrics survey software from each participant prior to initiation of study tasks. Study personnel will obtain informed consent from participants and answer questions about the study or informed consent process prior to beginning study activities. Following informed consent, participants will complete a demographics questionnaire through Qualtrics that also includes items assessing history of suicide attempts from the Self-Injurious Thoughts and behaviors Interview (Nock, Holmberg, Photos, & Michel, 2007) for study eligibility determination and randomization purposes as well as the Suicide Visual Analog Scale (Bryan, 2019). Regardless of eligibility, all participants will be provided with contact information for crisis resources including the National Suicide Prevention Lifeline and Veterans Crisis Line.

3.5. Randomization to Study Conditions.

REDCap, a secure online survey and data management system maintained by The Ohio State University, will be utilized to randomize participants to study conditions immediately after obtaining demographic information (man, woman, other) and information about suicide attempt history (no suicide attempts, one suicide attempt, more than one suicide attempt) obtained from the SITBI). Participants will be randomized using stratified blocks of 6 or 8 participants, per recommendations by Krenan et al. (1999). After randomization, each participant will complete the remainder of the research study, but will be presented with one of the following pages containing instructions for completing the MMPI-2-RF-EX.

MMPI Condition 1 (Standard Instructions): “We want you to imagine that you are undergoing psychological testing as part of standard intake procedures for receiving services in a mental health clinic, which involves completing some questionnaires and a personality test before the first session. Please answer the questionnaires as honestly as you can, as your mental health care provider will use the results of your testing to develop your treatment plan. Please note, the questionnaire has some “lie” scales built into it that detect false responding. Additionally, as part of the intake process, you agreed to identify questions that you think are assessing your current risk of suicide. You will open the link to this portion of the study that was sent to you by study personnel to complete this.”

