MMPI Condition 2 (Simulated Underreporting): “We want you to imagine that you are undergoing testing as part of standard intake procedures for receiving services in a mental health clinic, which involves completing some questionnaires and a personality test before the first session. You have recently had recurring thoughts of suicide and have thought of ways to attempt suicide. However, you are concerned that you will be hospitalized if you disclose this during testing and do not want to be hospitalized. Please answer the questionnaires as though you are trying to hide or downplay any thoughts of suicide or intent to make a suicide attempt. The questionnaire has some “lie” scales built into it, so try to avoid being detected. If you are able to avoid detection, you will receive an additional \$20 gift card. Additionally, as part of the intake process, you agreed to identify questions that you think are assessing your current risk of suicide. You will use a computer to mark these while taking the questionnaires.”

3.6. Additional incentives following completion of the first portion of the study.

Following the study session, all participants will receive payment in the form of \$50 for participation. Additional incentives are condition-dependent, will be described to participants at the beginning of the study as part of the informed consent process, and administered no later than two weeks following completion of the study protocol:

Simulated Underreporting: Additional payment for undetected underreporting on MMPI-2-RF-EX. Individuals in the Simulated Underreporting condition who do not produce clinically significant MMPI-2-RF-EX K or L scale elevations and are classified as Simulation Compliant based on Posttest Inquiry responses will receive an additional electronic \$20 gift card through email, following recommendations and procedures outlined in previous research (Brown & Sellbom, 2020; Crighton et al., 2017).

3.4. Detailed Study Procedures. One hundred and fifty adult military Veteran participants residing in the United States will complete eight study components during the baseline study session:

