consenting, demographics survey and self-reported history of suicide attempts, randomization to study conditions, the MMPI-2-RF-EX, self-report measures, and the post-test survey to assess compliance with study instructions. Consenting procedures will always be completed first, and demographic and suicide attempt history data will always be collected second for randomization to conditions in both components of the study through REDCap online software. We estimate that the total participation time will be approximately 2.5 hours (2 hours to complete the MMPI-2-RF-EX and extra-test self-report measures. In order to protect participant confidentiality, password-protected Zoom or phone-based sessions will be conducted during the baseline session, in order to ensure security of MMPI-2-RF-EX items. All data will be collected through the Qualtrics, and non-PHI demographic information will be entered into REDCap system for randomization purposes. ID numbers will be linked to all data collected in the study, including identifying information collected in a separate data set as part of safety procedures (See Section 3.7), which will be deleted at the conclusion of the study. All deidentified data will be downloaded and deleted from Qualtrics servers at the conclusion of the study and stored on the password protected OneDrive server hosted by OSU indefinitely for the proposed analyses and secondary analysis. Additionally, in order to protect participant privacy during the study, all study personnel will conduct study procedures from a private location, using a secure Internet connection and instruct all participants to do the same, if possible, and outline the risks of loss of privacy or confidentiality if the participant is unable to do so.

3.7. Internal Validity. A number of measures will be implemented to mitigate threats to internal and external validity. Specifically, the randomization procedures employed in the proposed research study (See Section 4.1.2) were selected to account for the potential influences of gender and suicide attempt status on study findings.

3.8 Data Analysis.

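### Does the Crisis Response Plan aim, stated in the objectives but never developed, require a change to the plan?

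*Combined protocol and SAP*

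**What the plan says.** Section 1 numbers two aims. The first concerns the MMPI-2-RF-EX validity scales. The second is to "compare the use and preliminary effectiveness of a self-administered version of the Crisis Response Plan (CRP") with a clinician-administered version, looking for less suicidal or death ideation, less distress and more positive affect.

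Several later places speak as if the study had two parts. Section 3.1 says "For both components of the study, participants will be randomized using stratified blocks of 6 or 8 participants". The heading of section 3.6 is "Additional incentives following completion of the first portion of the study". Section 3.9 mentions agreement to both portions and describes what both versions of the Crisis Response Plan (CRP) will contain.

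The design that is spelled out is the MMPI simulation alone. Section 3.2 has 150 Veterans "randomized to study conditions (75 in the Simulation condition and 75 in the Standard condition"). Section 3.5 prints two instruction sets and no others. The Detailed Study Procedures (the second section numbered 3.4) state that participants "will complete eight study components during the baseline study session" and then name "consenting, demographics survey and self-reported history of suicide attempts, randomization to study conditions, the MMPI-2-RF-EX, self-report measures" and a post-test survey. Section 3.8.1 plans one MANOVA and two hierarchical regressions, all on the contrast between the Standard and Simulated groups.

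**The concern.** An approved objective that nothing in the methods can answer is normally a serious fault. Here the reader is promised a comparison of two ways of delivering an intervention, and the document gives no arms, no delivery step, no assessment afterwards and no test. If a CRP comparison were later reported under this document, its arms, outcomes, timing and analysis would all have been chosen without prespecification. A reader might also assume that the power statement in section 3.2 covers it.

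The safety text adds to the unease. Section 3.9 describes a CRP carrying crisis contacts, yet no listed procedure delivers one.

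**Working it through.** **1. What the document supplies for the second aim.** Counts from the text:

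| Element | Defined | Of which CRP |
|---|---|---|
| Conditions (3.5) | 2 | 0 |
| Hypotheses (section 1) | 3 | 0 |
| Planned analyses (3.8.1): 1 MANOVA + 2 regressions | 3 | 0 |
| Session components listed (Detailed Study Procedures) | 6 or 7 | 0 |

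The component count is 6 if demographics and attempt history are one item, and 7 if they are two.

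**2. Whether existing measures could stand in.** The Beck scale and the Suicide Cognitions Scale bear on ideation and suicidal thinking, but section 3.8.1 assigns them to the simulation contrast. They are completed after half the sample has been told to hide suicidal thoughts. The attempt-history items are collected "for study eligibility determination and randomization purposes as well as the Suicide Visual Analog Scale", so that rating precedes randomization and the instructions. It is described once, with no repeat. No instrument is designated for distress or positive affect. The second aim therefore cannot be answered from this document.

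**3. Whether the stated power depends on the second aim.** Section 3.2 claims .98 to .99 for medium effects in all regression-based analyses. The figure is printed as β and makes sense only as power. Assumptions: f² = 0.15 for medium, α = 0.05, and fixed-model linear regression as an approximation, since the outcome is group membership.

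Power = 1 − F(F_crit; u, N − p − 1, λ), where F is the noncentral F distribution function, λ = f²N, u is the number of predictors tested and p the number in the model.

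- N = 150: λ = 0.15 × 150 = 22.5. For u = p = 2, power is 0.992. For u = 1, p = 2 (the second step of each K/L model), it is 0.997. For u = p = 3, it is 0.985.
- After about 15% loss: 150 × 0.85 = 127.5, say 128, and λ = 0.15 × 128 = 19.2. Power is 0.979 for u = p = 2 and 0.991 for u = 1, p = 2.

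The stated range is reproduced by the K and L regressions. No CRP regression is specified, so removing the second aim leaves the figure where it is.

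**4. Whether that figure could be borrowed for a CRP comparison.** It could not. As an illustration only, assume one post-score comparison, d = 0.5 and two-sided α = 0.05, with noncentrality d√(n/2). With 75 per arm this is 0.5 × √37.5 = 3.06 and power is 0.86. With 64 per arm it is 0.5 × √32 = 2.83 and power is 0.80. With 37 to 38 per arm (half taking part) power is 0.56 to 0.58. The document makes no such claim for the second aim, so there is no wrong figure to correct.

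**5. What each remedy would alter.** Deleting the aim and its related wording leaves the conditions, allocation, sample size, measures, hypotheses and analyses as they are. Pointing to a separate CRP plan leaves them as they are too. Neither changes a number that this study will report.

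**The case for a change.** The strongest case for a change is that the objectives bind the report. One of two numbered aims has no route to an answer, the aim is not marked as deferred or documented elsewhere, and correcting the wording costs little. The factual part of this stands in full. So does the warning that a CRP result could not be called prespecified on the strength of this document.

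The proposed remedy of removing the aim is less secure. It assumes that the component was dropped, and no section says so. The background in section 2 refers to two of the study's aims, both about the MMPI, which implies at least one more. Section 3.9 treats agreement to both portions as something that varies between participants. The measures and the session are called baseline. All this fits a second component run under its own document as well as it fits leftover text. A cut would also have to reach the intervention rationale in section 2 and the reference to treatment in section 2.3.

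Some supporting signs carry little weight:

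- **Eight components.** The missing item or items are not identified. The separate item-marking task or the Suicide Visual Analog Scale could account for one.
- **Session time.** The estimate reads "total participation time will be approximately 2.5 hours (2 hours to complete the MMPI-2-RF-EX and extra-test self-report measures". The remaining 2.5 − 2 = 0.5 hour can plausibly be taken up by consent, demographics, randomization and the post-test survey.
- **Uncited references.** Three crisis-response-planning papers and one affect-scale paper are never cited in the text, but neither are at least four other entries, among them a depression-screening validation and the MMPI-2-RF technical manual.

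On safety, the contact details, alternate contact, three risk questions, emergency services and crisis contacts in section 3.9 do not depend on a CRP. The CRP sentence there and the listed procedures do not agree and must be reconciled by the sponsor. That does not bear on the statistical plan.

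**Conclusion.** The document contradicts itself about the CRP, but no change to the plan follows. The second aim has 0 of 2 conditions, 0 of 3 hypotheses, 0 of 3 analyses and no post-CRP measure. An analyst following section 3.8 would run the MANOVA and the two regressions and report nothing on the CRP, which is the correct outcome when no such data are collected under this document. The effect on the MMPI hypotheses, on their power (.98 to .99 as stated; 0.979 to 0.997 recomputed for the K/L models at N = 128 to 150) and on the randomization is nil.

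This rests on two assumptions. The first is that the report confines its conclusions to what was measured. The second is that any CRP comparison in these Veterans has its own arms, outcomes and analysis set out elsewhere. The document does not show whether such a plan exists. If a CRP conclusion were drawn from this document alone, the judgement would be different. Otherwise, aligning section 1 and the two-part wording in sections 3.1, 3.6 and 3.9 with the listed procedures is housekeeping that alters no result.
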